## **STUDY PROTOCOL:**

The study was designed as a prospective, randomized, two-arm, parallel, unblinded study, during which We will include 138 couples (69 in each group) of IVF / ICSI users. Cycles canceled or without transfer (either due to not obtaining oocytes, non-fertilization or arrest of embryonic development) will not be included in the study. The assignment of the pairs to each of the groups will be carried out by means of a random sampling procedure. The randomization list will be created specifically for this project and will be guarded by an outsider to the research team:

- Group I (experimental): fresh transfer is not performed, the best quality embryo is cryopreserved. Elective transfer in a later cycle of the cryopreserved embryo.
- Group II (control): fresh transfer of the best quality embryo.

Couples will be able to participate in the study for only one cycle. Each couple will be interviewed by a member of the team who will explain the characteristics of the study and they will be given an Information Sheet. It is necessary to obtain the written informed consent of each couple. The person outside the investigation team who is guarding the randomization list will assign the corresponding treatment group.

Before starting the study, ethical approval will be processed by the Ethics Committee through the Ethics Portal of the Biomedical Research of Andalusia.

Patients must follow ovulation stimulating treatment, in order to achieve multiple follicular development. A "long analog" GnRH agonist protocol will be used. This consists of administering from the day 22 of the cycle 0.1 mg / day of GnRH analog (Decapeptyl 0.1; Lasa, Barcelona, Spain) until the day the gonadotropin administration, in which the dose is reduced to 50% until the day of hCG. After 10-14 days of administration of the agonist, we proceed to check the pituitary braking by means of ovarian vaginal ultrasound (absence of follicles and cysts). Then, 300 IU of recombinant FSH (rFSH) is administered per day (Gonal F, Merck, Madrid, Spain) for two days, and 150 IU of FSHr from the 3rd to the 7th day. On this day, ultrasound control of the follicular development is accomplished in order to re-adjust the dose of rFSH to each patient. Once the follicular response is adequate (more than 3 ovarian follicles greater than 18 mm in diameter), we proceed to trigger ovulation using 6500 IU hCG (Ovitrelle, Merck, Darmstadt, Germany).

Oocyte retrieval will be performed by transvaginal ultrasound-guided follicular puncture 36 hours after the injection of hCG, anticipating the ovulatory process, using an ovarian puncture needle (Labotect LaborTechnik-Göttingen, Göttingen, Germany). The follicles larger than 17 mm are punctured one by one, aspirating their content into fluid collection tubes.

The content of the aspirated follicle should be transported quickly to the laboratory to immediately check for the presence of the cumulus-oocyte complex. Antibiotic prophylaxis is not routinely performed, and only in cases where the puncture is more difficult, a single dose of 1,500 mg of cefuroxime sodium will be administered intravenously (Cefuroxime Normon EGF, Madrid, Spain) or 1000 mg of erythromycin lactobionate (Pantomycin Abbot, Madrid, Spain) in patients allergic to beta-lactams. Once the follicular fluid (FF) arrive at the laboratory, the search and identification of the cumulus-oocyte complexes is performed by locating them under stereomicroscopic vision in a 100x15 mm Petri. They are placed in a new 35x10 mm Petri dish inside a few drops of MOPS culture medium Vitrolife (IVF Science Scandinavia, Gothenburg, Sweden) previously aerated and heated to 37°C, to eliminate the remains of FF.

IVF/ICSI and embryo culture will then be performed. To perform sperm microinsemination (ICSI) it is necessary to remove the cumulus and corona radiata from the oocyte. To decumulate, the crown-oocyte cluster complex is submerged in a solution with 80 IU / mL hyaluronidase (HYASE, IVF Science Scandinavia, Gothenburg, Sweden) for 10-20 seconds aspirating the complex several times using a pasteur pipette. The microinsemination technique is performed under a microscope inverted with Eppendorf and Narishigue micromanipulators and microinjectors. In Vitro Fertilization (IVF) is performed in a five-well plate, depositing 0.5 mL of IVF medium (Vitrolife, Sweden) and 0.5 mL of Ovoil (Vitrolife, Sweden) in each well. Five clusters are left per well and 100,000 sperm/mL are added.

In both cases, the oocytes are cultured in a Thermo-Fisher incubator, within a morphokinetic platform (PrimoVision). The following days are evaluated for their classification, choosing the one of better implantation potential according to the division times measured by morphokinetics and the morphological criteria of the Spanish Association for the Study of Reproduction Biology (ASEBIR) reviewed in 2015.

The embryo transfer will be carried out in group 2 on the third day, choosing the best embryo according to the previous criteria. In Group 1 embryos will be cryopreserved by vitrification, selecting the best one for deferred transfer. The commercial vitrification media will be Medicult Vitrification, and the storage device will be Cryoleaf (McGill Cryoleaf, Medicult, Denmark). All cryopreserved embryos will be stored in liquid nitrogen at -196°C in storage cylinders (Air Liquide, France). The day before cryotransfer, the embryo is devitrified, using the thawing kit (Medicult Warming, Denmark). At the end, the embryos are washed in G2 medium (Vitrolife), leaving them in cultivation until the following day, after evaluation of embryonic quality and cryosurvival (percentage of lysed cells). The endometrium of the woman is prepared by treatment with estradiol valerate and progesterone. The day of the cryotransfer embryonic quality is assessed again, emphasizing embryonic division. Cryotransfer is done by the same technique than fresh transfer.

Workplan:

First year:

- Our center is routinely able to carry out the vitrification, so it is not necessary to fine-tune our techniques.
- Design of the Access database with the variables to be analyzed.
- Beginning of the interviews and selection of patients
- Beginning of the IVF/ICSI cycles and cryotransfers.

Second year:

- Continue with the selection of patients until completing the expected number.
- Continuation of IVF/ICSI cycles and cryotransfer.
- Carry out an intermediate analysis of the data using "adaptive clinical designs".

Third year:

- Continuation of IVF/ICSI and cryotransfer cycles.
- Collection of data from IVF/ICSI and neonatal cycles and application of statistical treatment.
- Drafting of results

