## **STATISTICAL ANALYSIS PLAN**

For the purpose of testing the null hypothesis that shows equal live birth rates in the group of women who undergo elective deferred transfer of a single embryo and the group that undergoes elective transfer of a fresh embryo, a power of 80% has been established to detect statistically significant differences using a bilateral Chi-square test for two samples, taking into account that the significance level is 5%, and assuming that the proportion in the group of women undergoing a fresh transfer is 50.9%, the proportion in the group of women undergoing elective deferred transfer is 78%, and that the proportion of women out of the total is 50%, it will be necessary to include 48 women in each group, for a total of 96 experimental units in the study.

Taking into account that the expected dropout rate is three out of ten women, it will be necessary to include 69 women per group.

The assignment of the 138 women to one of the groups will be carried out by a randomized procedure, following a sequence of random numbers generated by specific software (Epidat, Epidemiological Analysis of Tabulated Data Program. Tabulated. Version 3.1)

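### No analysis set keeps all randomised couples, so Group I failures after allocation (warming, overnight culture, non-return) can drop out of the live-birth denominator

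*Combined protocol and SAP*

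**What the plan says.** The study protocol's design paragraph sets the exclusion: "Cycles canceled or without transfer (either due to not obtaining oocytes, non-fertilization or arrest of embryonic development) will not be included in the study". It defines Group I by "Elective transfer in a later cycle of the cryopreserved embryo", while Group II has a fresh transfer on the third day. On assignment it says only that "The person outside the investigation team who is guarding the randomization list will assign the corresponding treatment group". That sentence follows the description of interview and consent, but it is not placed relative to stimulation, retrieval or day 3.

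The laboratory section adds steps that only Group I goes through. "In Group 1 embryos will be cryopreserved by vitrification, selecting the best one for deferred transfer". Embryos are later warmed, with the protocol "leaving them in cultivation until the following day, after evaluation of embryonic quality and cryosurvival (percentage of lysed cells"), and quality is assessed again on the day of transfer.

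The SAP states the null hypothesis in terms of "live birth rates in the group of women who undergo elective deferred transfer of a single embryo", against those who undergo fresh transfer. On numbers it says "it will be necessary to include 48 women in each group, for a total of 96 experimental units in the study", and then "Taking into account that the expected dropout rate is three out of ten women, it will be necessary to include 69 women per group". It defines no analysis set, no denominator for the live-birth rate, and no rule for a couple whose birth outcome is unknown.

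**The concern.** A randomised comparison is protected only if couples are counted in the arm to which they were allocated, whatever happens afterwards. Here the exclusion of cycles without transfer and the transfer-based hypothesis both point towards a denominator of transfers.

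That matters because the arms do not face the same risks after allocation. A Group II couple with a usable day-3 embryo goes straight to transfer. A Group I couple must also have an embryo survive vitrification, warming and overnight culture, and must come back in a later cycle. Failure at any of these steps is part of what choosing deferral means for the couple. If such couples are removed, the deferred arm is judged only on those who got through, and its live-birth rate rises for a reason unrelated to benefit.

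The study is unblinded and the second-year workplan includes an intermediate analysis. If the rule is left open, the decision on which couples count could be taken with results in view.

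**Working it through.** **1. The plan's own sample size.** Inputs from the SAP: 50.9% fresh, 78% deferred, two-sided 5%, 80% power, equal groups. Pooled-variance formula with mean rate 0.6445:

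n = [1.960 × √(2 × 0.6445 × 0.3555) + 0.8416 × √(0.509 × 0.491 + 0.78 × 0.22)]² / 0.271²
= [1.960 × 0.6769 + 0.8416 × 0.6492]² / 0.07344 = 47.8, so 48 per group.

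Dropout: 48 / 0.7 = 68.6, so 69 per group. Both figures reproduce.

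**2. What the inflation implies.** 138 − 96 = 42 women (30.4%), or 21 per group, assigned but not in the number on which the test is sized. The SAP does not state this as an exclusion, and it gives no cause, arm or timing for the 30%.

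**3. Which losses can differ by arm.**

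| Loss | Arm | Relative to allocation |
|---|---|---|
| No oocytes, no fertilization, arrest by day 3 | Both, expected similar | Not determinable |
| Failure at warming or overnight culture | Group I only | After |
| Not returning for the later cycle (inferred from the design) | Group I only | After |
| Birth outcome unknown after transfer | Either | After |

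**4. Size if Group I-only failures are excluded.** Assume no true difference, 50.9% per couple in both arms, and a fraction f of Group I with no transfer. The documents give no value for f. The apparent Group I rate is 0.509 / (1 − f). Rejection is by exact binomial enumeration of the two-sided Pearson chi-square at 5%, with 48 controls.

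| f | Group I n | Apparent rate | Bias | Rejection |
|---|---|---|---|---|
| 0 | 48 | 50.9% | 0 | 5.2% |
| 5% | 46 | 53.6% | +2.7 points | 5.7% |
| 10% | 43 | 56.6% | +5.7 points | 8.6% |

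Within the plan's own allowance (48 v 48 analysed), if 3 of Group I's 21 losses are no-transfer failures and the rest are random, f = 3/69 = 4.3%, with +2.3 points and 5.8% rejection. If 7 of 21, f = 10.1%, with +5.7 points and 8.9%.

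**5. Offsets.** If Group II also loses couples, the biases partly cancel. With 10% lost in Group I and 5% in Group II: 0.509/0.90 − 0.509/0.95 = +3.0 points (6.3% rejection). Swapping the two reverses the sign. If a spare vitrified embryo replaces half of the failures, f = 10% acts like 5%.

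**6. Unknown births.** With m unknown per arm of 69, the observed difference can move over a range of 2m/69: 8.7 points for m = 3, 20.3 for m = 7. Counting unknowns as no live birth is not neutral either. If 5% are unknown in Group I only, its rate falls by 0.509 × 0.05 = 2.5 points under the null (6.0% rejection, 69 v 69).

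**7. Power per couple randomised, 69 per arm all analysed.** If 50.9% and 78% are per-transfer rates (the SAP does not say):
- no loss: 92%;
- 10% without transfer in both arms (45.8% v 70.2%): 83%;
- Group I only, 5% (50.9% v 74.1%): 81%;
- Group I only, 10% (50.9% v 70.2%): 64%.

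**The case against.** The strongest reply is that the exclusion sentence is an eligibility rule. Its three listed causes all arise by day 3, before the arms diverge. If couples are allocated only once a transferable embryo exists, the sentence removes nobody who was randomised. The workplan's intention to go on selecting patients until the expected number is reached is compatible with this: excluded cycles might be replaced and not count towards 138. This stands for the listed causes, and it is why the allocation point must be stated before the sentence is changed. It does not reach warming failure, non-return or unknown births, which follow allocation on any reading and have no rule.

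Three stronger readings are tempting and are not supported:
- **That the plan definitely discards Group I failures.** The parenthesis does not name them. The words on cycles without transfer can be read to cover them, but the text does not settle it.
- **That the plan states that 42 women will be left out.** It states a dropout rate. The 42 is implied by the inflation, which is routine practice.
- **That a serious bias has been shown.** Every f above is an assumption, non-return is nowhere mentioned, 5% has a negligible effect, and the sign can reverse.

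It is also fair to say that counting unknown births as no live birth is only one option. By the figures above it can bias about as much as the problem it would cure. What is needed is a rule fixed in advance.

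**Conclusion.** The concern holds in this form: the plan as worded allows a per-transfer primary comparison and names no set of all randomised couples. Its effect on losses that only Group I can suffer after allocation is undefined. If those losses are excluded, the bias is towards deferral. Its size is unknown; under the assumed null of 50.9% per couple it is negligible at 5% and +5.7 points with 8.6% rejection at 10%, before any offset.

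The need for correction rests on the undefined analysis set and not on an assumed loss rate. Two analysts could follow this text and report different denominators. A reader might infer that the sample size is wrong; it is not. The 48 and 69 reproduce, and the power question arises only once it is settled whether the two planning rates are per transfer or per couple.

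**What to change.** 1. State the point in the cycle at which allocation occurs.
2. Make the primary analysis all randomised couples in their allocated group, and reword the SAP hypothesis from women who undergo each transfer to women allocated to it. A couple known to have had no transfer after allocation, including failed cryosurvival, arrest after warming or non-return, counts as no live birth from the study cycle. The per-transfer comparison becomes secondary.
3. If allocation is before day 3, apply item 2 to the protocol's listed exclusions as well. If it follows confirmation of a transferable day-3 embryo, keep the exclusion sentence, labelled as a pre-randomisation eligibility rule only.
4. Pre-specify one rule for unknown birth outcomes after transfer, with a tipping-point sensitivity analysis over the possible splits in each arm.
5. Report no-transfer, non-return and unknown outcomes by arm and reason. Say what the 30% covers, whether 50.9% and 78% are per transfer or per couple, and the power per couple randomised.

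Cost: no new data are needed for couples known to have had no transfer, but birth outcomes after transfer must be followed up. If both planning rates are per transfer, restated power at 69 per arm may be lower than the 92% that applies with no loss: for example 83% with 10% no-transfer in both arms, or 64% with 10% in Group I only.

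### The plan does not say whether 138 is the number of couples randomised or the number reaching transfer, and its exclusion rule can drop couples after allocation

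*Combined protocol and SAP*

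**What the plan says.** In the opening paragraph of the study protocol: "We will include 138 couples (69 in each group) of IVF / ICSI users". The next sentence says that cancelled cycles and cycles with no transfer do not form part of the study. It lists three reasons: no oocytes obtained, failed fertilisation, and embryos that stop developing. A person outside the team holds the randomisation list and assigns the group. The point in the cycle at which this happens is not given.

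In the statistical analysis plan, 48 women per group (96 in all) are needed, and then "Taking into account that the expected dropout rate is three out of ten women, it will be necessary to include 69 women per group". The last paragraph adds: "The assignment of the 138 women to one of the groups will be carried out by a randomized procedure".

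In the workplan, under the second year: "Continue with the selection of patients until completing the expected number". The number is not specified.

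The documents do not define dropout, do not say whether a cancelled or no-transfer cycle counts towards the three in ten, and contain no rule for or against replacing a couple.

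**The concern.** The same figure has two meanings. Read with the exclusion sentence beside it, the protocol's 138 is a count of couples who reached a transfer. In the statistical analysis plan, 138 is a count of couples put through randomisation, some of whom are expected to be lost.

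Two things are at stake.

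- **Bias.** If the exclusion is applied to couples already allocated, the groups compared are no longer the groups randomised. In an unblinded trial where one arm has an extra step at which a cycle can fail, the couples removed need not be alike in the two arms. Removing failures from the deferred arm alone would raise its live birth rate.
- **Size.** A site cannot tell from the text when to stop allocating, and the power statement cannot be tied to a defined denominator.

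**Working it through.** **1. Reproduce the plan's figure.** Inputs from the statistical analysis plan: two-sided 5% level, 80% power, live birth 50.9% (fresh) and 78% (deferred), equal groups, two-sample chi-square test.

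n per group = [1.960 × √(2p̄(1 − p̄)) + 0.842 × √(p1(1 − p1) + p2(1 − p2))]² / (p2 − p1)²

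With p̄ = (0.509 + 0.78)/2 = 0.6445 and p2 − p1 = 0.271:

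- 1.960 × √0.4582 = 1.327
- 0.842 × √0.4215 = 0.546
- n = (1.873)² / 0.0734 = 47.8, rounded up to 48

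Dropout: 48/0.7 = 68.6, rounded up to 69 per group, 138 in all. Both figures match the plan. There is one inflation. A second one would give 48/0.7/0.7 = 98.0 per group, which appears nowhere.

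**2. Can the exclusion fall after allocation?** The study protocol has Group II transferred on the third day, while Group I embryos are vitrified. The arm must therefore be known by day 3 at the latest.

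| Allocation | Listed failures before day 3 | Failure after warming (Group I only) |
|---|---|---|
| Early, for example at consent | after allocation, both arms | after allocation |
| As late as day 3 | before allocation | after allocation |

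Group I embryos are later warmed, checked for cell survival, cultured overnight and reassessed for division. A cycle that ends there has no transfer, so the exclusion reaches it under either timing. The documents do not say how often this happens, or whether another stored embryo would be used.

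**3. What each meaning of 138 implies.**

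Power = Φ{[(p2 − p1)√n − 1.960√(2p̄(1 − p̄))] / √(p1(1 − p1) + p2(1 − p2))}

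- *138 randomised, 30% lost from analysis:* 138 × 0.7 = 96.6, about 48 per group, power about 80%.
- *138 left after exclusions, no further loss:* 69 per group, power 92.3%. A further loss of 10%, 20% or 30% gives 89.4%, 85.5% or 80.4%.

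Couples to allocate so that 138 remain, at assumed exclusion rates:

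- 10%: 138/0.9 = 153.3, so 154
- 20%: 138/0.8 = 172.5, so 173 (174 for equal arms)
- 30%: 138/0.7 = 197.1, so 198

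**4. Power if all 138 are analysed as allocated.** Here the plan's rates are taken as rates among couples with a transfer. An assumed fraction f of each arm has no transfer and counts as no live birth. All 69 per group contribute.

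| f (assumed) | Fresh, 0.509(1 − f) | Deferred, 0.78(1 − f) | Power, 69 per group | n per group for 80% |
|---|---|---|---|---|
| 10% | 45.8% | 70.2% | 83.5% | 64 |
| 20% | 40.7% | 62.4% | 72.7% | 83 |
| 30% | 35.6% | 54.6% | 61.2% | 107 |

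**The case against.** The strongest reply is that the passages may agree. All three listed reasons can arise before the arms part on day 3. If couples are allocated only once an embryo is available, those cycles are never randomised, and 138 included equals 138 assigned. The plan does not state the timing. The protocol mentions assignment before it describes stimulation, but the order of the text is not a stated time point.

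This stands for failures before day 3. It does not cover a Group I embryo that fails after warming, which comes after allocation whenever allocation is done.

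A reader might also infer three stronger things, which the documents do not support:

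- **That excluded couples are replaced.** No sentence says so. The workplan line is a timeline item and fits recruiting until 138 are randomised. Replacement is possible under the protocol wording, but it is not a stated practice.
- **That losses are allowed for twice.** The calculation inflates once, and dropout is undefined. If the 30% covers only later losses, keeping cancelled cycles outside the 138 is not double counting. If it does cover them, the result is a larger trial (92.3% power at 69 per group), not an underpowered one.
- **That the next couple's arm becomes predictable.** This needs vacated list numbers to be reused, which the plan does not say. The list is held by someone outside the team.

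**Conclusion.** The concern holds as an unreconciled definition together with an exclusion rule that can act after allocation. Two parts rest on the text alone: 138 is not fixed as either randomised or reaching transfer, and failure after warming is a route out of the study open only to the experimental arm.

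The sizes rest on assumptions, because the plan gives no cancellation or no-transfer rate. At 10% to 30%, keeping 138 after exclusions means allocating 154 to 198 couples. Analysing 138 as randomised gives power from about 83% down to 61%. The power figures assume the same no-transfer rate in both arms, no other missing outcomes, and planning rates that apply per transfer. The direction and size of any bias from the Group I route cannot be computed from the documents.

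This should be settled in the text before the analysis. The point does not show the sample size arithmetic to be wrong.

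**What to change.** In the study protocol's opening paragraph:

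- limit the exclusion to cycles that fail before allocation;
- state that 138 is the number of couples randomised, that allocation closes at the 138th, that no couple is replaced and that no list number is reissued;
- state when in the cycle allocation takes place.

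In the workplan, name the target as 138 couples randomised.

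In the statistical analysis plan:

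- analyse every allocated couple in its assigned group, with no transfer counted as no live birth;
- say what the 30% covers. Under this rule a couple without a transfer has a known outcome and is not missing, so the allowance should refer only to couples whose outcome is unknown;
- restate the power, with the assumed no-transfer rate given.

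The cost is a few sentences and no couples beyond the 138 already planned. There are two drawbacks. The number reaching transfer is no longer guaranteed to be 69 per arm. The 80% claim may also not survive: on the assumptions above it holds at a 10% no-transfer rate but not at 20%, where 83 per group would be needed. The sponsor would have to accept the lower power or enlarge the trial openly.
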